6.3. Adjustments for Covariates

The randomization to treatment groups in the originating studies is stratified by disease severity (IGA) and geographic region. For Period 1, the covariates used in the logistic model for categorical data will include the baseline value from the originating study. When an MMRM analysis is performed, baseline value from originating study and baseline-by-visit interactions will be included as covariates. Unless otherwise specified, the statistical analysis models will adjust for these stratification variables. For Period 2, the covariates used in the logistic model for categorical data will include the baseline value from Week 52.

The baseline value from Study JAHN will be used as a covariate in the ANCOVA model for continuous safety data.

6.4. Handling of Dropouts or Missing Data

Intercurrent events (ICH E9 R1) are events which occur after randomization such that subsequent data (collected after the intercurrent event) are difficult to interpret.

Depending on the estimand being addressed, different methods will be used to handle missing data as a result of intercurrent events. Intercurrent events can occur through the following:

- application of the censoring rule (including after permanent study drug discontinuation or for responders and partial responders [on Placebo or baricitinib 1-mg] who are rescued to a higher dose [baricitinib 2 mg or baricitinib 4 mg])
- retreatment after downtitration or early withdrawal
- discontinuation
- missing an intermediate visit prior to discontinuation or rescue
- lost to follow-up

Noncensor intercurrent events are events that are not due to the application of any censoring rule (ie, the last 3 items in the list above).

Note that as efficacy and health outcome data can accrue after a patient permanently discontinues study drug or is rescued to either baricitinib 2 mg or baricitinib 4 mg (for responders and partial responders on placebo or baricitinib 1 mg), a censoring rule will be applied to all efficacy and health outcome observations subsequent to these events depending on the estimand being addressed.

The *Period 1 censoring rule* will censor efficacy after permanent study drug discontinuation or for responders and partial responders (on placebo or baricitinib 1 mg) who are rescued to a higher dose (baricitinib 2 mg or baricitinib 4 mg). This censoring rule will be applied to all efficacy endpoints conducted for the responder, partial responder, and nonresponder mITT populations (defined in Section 6.2.1). For responders and partial responders, the censoring rule will censor efficacy data after permanent study drug discontinuation or rescue date, whichever occurs first. For nonresponders, the censoring rule will censor efficacy data after permanent study drug discontinuation.

The *Period 2 censoring rule* will censor efficacy data after permanent study drug discontinuation or after retreatment, whichever occurs first. This censoring rule will be applied to efficacy endpoints and safety conducted for the Period 2 population corresponding to the withdrawal and downtitration substudy.

For patients treated in Period 2 but not eligible that enter the withdrawal and downtitration substudy, the censoring rule will censor efficacy data after permanent study drug discontinuation or rescue date, whichever occurs first.

Table JAHN.6.2 summarizes the various imputation techniques being used for select efficacy analyses. Sections 6.4.1 through 6.4.3 summarize the imputation methods.

Table JAHN.6.2. Imputation Techniques for Various Efficacy Variables

Population	Endpoints ^a	Imputation Method ^b
Responder and partial responder mITT Period 1	IGA(0,1), IGA(0,1,2), EASI75, 4-point Itch NRS improvement	NRI mLOCF ^c
	Exploratory endpoints	NRI (categorical endpoints) mLOCF ^c
Nonresponder mITT Period 1	IGA(0,1), IGA(0,1,2), EASI75, 4-point Itch NRS improvement	NRI mLOCF ^c
	Exploratory endpoints	NRI (categorical endpoints), MMRM (continuous endpoints) mLOCF ^c
Randomized Downtitration Withdrawal Substudy Population Period 2 nonsubstudy population Open label Period 2 non-substudy population	IGA(0,1), IGA(0,1,2), EASI75, 4-point Itch NRS improvement	NRI mLOCF ^c
	Exploratory endpoints	NRI (categorical endpoints) mLOCF ^c

Abbreviations: EASI = Eczema Area and Severity Index; IGA = Investigator's Global Assessment for atopic dermatitis; mITT = modified intent-to-treat; mLOCF = modified last observation carried forward; MMRM = mixed-model repeated measures; NRI = nonresponder imputation; NRS = Numeric Rating Scale.

^a Refer to [Table JAHN.6.6](#) and [Table JAHN.6.8](#).

^b All analysis with censoring.

^c mLOCF will be used as Primary analysis in/after Feb2021 DBL.

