
Patients Retreated during Substudy To evaluate the ability to recapture efficacy based on clinical measures after experiencing a loss of treatment benefit:
	
 • Proportion of patients with a response of IGA 0, 1, or 2 within 16 weeks of retreatment • Proportion of patients with a response of IGA 0 or 1 within 16 weeks of retreatment • Proportion of patients with a response of EASI75 from baseline of originating study within 16 weeks of retreatment

Patients Not Entered into the Substudy To evaluate the effect of maintaining baricitinib dose on clinical measures.
	
 • Proportion of patients with a response of IGA 0, 1, or 2 assessed at Week 104 • Proportion of patients with a response of IGA 0 or 1 assessed at Week 104 • Proportion of patients with a response of EASI75 from baseline of originating study assessed at Week 104

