For the DBL in December 2021 and final DBL, the following analysis populations are defined for efficacy and health outcome analyses.

Randomized Downtitration Withdrawal Substudy Population: All patients (including open-label patients) who are rerandomized at Week 52, enter the substudy, and receive at least 1 dose of the IP in Period 2.

Re-Treatment Substudy Population: A subset of Randomized Downtitration Withdrawal Substudy Population who experience IGA ≥ 3 at any time in Period 2 and receive at least 1 dose of retreatment of the original dose.

Period 2 Nonsubstudy Population: All patients randomized at Week 0 of main Study JAHN (excluding open-label patients) who are not eligible to enter the substudy at Week 52 and receive at least 1 dose of the IP in Period 2.

Open-Label Period 2 Nonsubstudy Population: All patients enrolled in the open-label addendum who are not eligible to enter the substudy at Week 52 and receive at least 1 dose of the IP in Period 2.

Long-Term Baricitinib 4 mg Population: Patients initially randomized to baricitinib 4 mg in the originating studies and remain on 4-mg up to Week 52 of Study JAHN. At Week 52 of Study JAHN, patients also need to continue 4-mg and receive at least one dose in Period 2 regardless of eligibility of entering sub-study.

Safety population: For the purpose of Study JAHN alone, the safety population is defined as all patients who received at least 1 dose of IP in Study JAHN and who did not discontinue from the study for the reason ‘Lost to Follow-up’ at the first postbaseline visit in Study JAHN. For the safety analysis of Treatment Period 2, patients with at least 1 dose of IP in Treatment Period 2 will be included in the safety analysis of Treatment Period 2.

Safety analyses will be performed using the safety population and will be analyzed according to the following treatment groups (or cohorts) defined in [Table JAHN.6.1](#). Patients will be analyzed according to the dosing regimen to which they were assigned.

Table JAHN.6.1. Safety Population Treatment Groups

Treatment Groups for Treatment Period 1 (Week 0-52)	Definition
PBO	Placebo at entry to Study JAHN followed to end of Treatment Period 1 or censored at treatment change
BARI 1 mg	BARI 1 mg followed to end of Treatment Period 1 or censored at dose or treatment change
PBO/BARI 1 mg to BARI 2 mg	PBO/BARI 1 mg switching to BARI 2 mg at entry to Study JAHN followed to end of Treatment Period 1 or censored at dose or treatment change

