SCORing Atopic Dermatitis	Change from baseline in SCORAD score	mITT population from open-label study	Descriptive using observed and mLOCF	Weeks 0-52	Exploratory

Measure	Variable	Population ^a (Section 6.2.1)	Analysis Method ^b (Section 6.2.3)	Time Point	Analysis Type
(SCORAD) ^c	Percent change from baseline in SCORAD score	Period 2 non-substudy population Open-label Period 2 non-substudy population	Descriptive using observed and mLOCF	Weeks 52-200	Exploratory
	SCORAD score, Pruritus & Sleep Loss Percent change from baseline in SCORAD score, Pruritus & Sleep Loss	Long term Baricitinib 4 mg population	Descriptive using observed and mLOCF	Weeks 52-200	Exploratory
	Proportion of patients achieving SCORAD75 Proportion of patients achieving SCORAD90	mITT population from originating combination therapy study - responders, partial responders	Descriptive using NRI and mLOCF	Weeks 0-52	Exploratory
		mITT population from originating combination therapy study - nonresponders	Logistic regression using NRI Descriptive using mLOCF	Weeks 0-52	Exploratory
		mITT population from open-label study	Descriptive using NRI and mLOCF	Weeks 0-52	Exploratory
		Period 2 non-substudy population Open-label Period 2 non-substudy population	Descriptive using observed, NRI and mLOCF	Weeks 52-200	Exploratory
		Long term Baricitinib 4 mg population	Descriptive using NRI, observed and mLOCF	Weeks 52-200	Exploratory

Abbreviations: AD = atopic dermatitis; ANCOVA = analysis of covariance; Bari = baricitinib; DBL = database lock; EE = efficacy evaluable; Feb = February; mITT = modified intent-to-treat; mLOCF = modified last observation carried forward; MMRM = mixed-model repeated measures; NRI = nonresponder imputation.

- ^a Populations from originating studies for reporting periods of Weeks 0-52 are on the mITT population; they are reported by responder status from originating study: responders, partial responders, responders + partial responders and nonresponders. Populations for visit-wise analyses for those who entered the randomized withdrawal and downtitration study are based on efficacy evaluable sets for each of Week 56, 60, 64, and 68 (defined in Section 6.2.1).
- ^b All categorical endpoints use NRI, unless otherwise stated.
- ^c Descriptive using observed data for the endpoints beyond Week 104, unless otherwise stated.

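### The Period 2 censoring rule has no exemption for retreated patients, so the secondary recapture endpoints lose all the data they rest on

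*SAP*

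**What the plan says.** **The objective.** SAP Section 4.2 has a secondary objective for patients retreated during the substudy: "To evaluate the ability to recapture efficacy based on clinical measures after experiencing a loss of treatment benefit". Its first endpoint is "Proportion of patients with a response of IGA 0, 1, or 2 within 16 weeks of retreatment". The other two are IGA 0 or 1 and EASI75 over the same 16 weeks. Section 6.11.2 promises a summary of these three responses in patients who need retreatment.

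**The population.** Section 6.2.1 defines the Re-Treatment Substudy Population as "A subset of Randomized Downtitration Withdrawal Substudy Population": those who reach IGA 3 or more in Period 2 and take at least one dose of retreatment.

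**The censoring rule.** Section 6.4 says the Period 2 rule will "censor efficacy data after permanent study drug discontinuation or after retreatment, whichever occurs first". It gives the scope in the next sentence: "This censoring rule will be applied to efficacy endpoints and safety conducted for the Period 2 population corresponding to the withdrawal and downtitration substudy".

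**The analysis row.** Table JAHN.6.5 has one recapture row, for IGA of 2 or lower. It is labelled secondary, runs from Week 52 to Week 200, and gives the method only as descriptive. Footnote b of that table reads "All categorical endpoints use NRI, unless otherwise stated". Section 6.4.3 makes mLOCF primary for all categorical endpoints from the February 2021 lock, and applies it after censoring.

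**The concern.** The substudy withdraws or lowers the drug and restores it on relapse. One purpose is to learn whether a lost response can be regained. Only assessments made after retreatment can answer that, and those are the assessments the Period 2 rule removes. The rule suits the comparison of rerandomised arms, where response after retreatment would blur the effect of withdrawal. It does not suit the recapture analysis, yet nothing in the SAP switches it off there.

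An analyst who follows the text would report either no recapture at all or no result. An analyst who follows the evident purpose must depart from a written rule without documented authority, and must choose the time origin and missing-data rule unaided. Two competent analysts could therefore report very different figures for a named secondary objective.

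**Working it through.** The plan states no recapture rate, sample size or power for this objective, so there is no figure of its own to reproduce. The check is to apply the written rules in order.

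**1. Is the recapture population inside the rule?** Yes. It is defined as a subset of the substudy population, and Section 6.4 applies the rule to that population's efficacy endpoints without exception.

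**2. What survives censoring?** Retreatment follows an IGA of 3 or more (SAP Section 5.1, note c to Figure JAHN.5.1). Values up to the retreatment date are kept and later ones are censored. Every assessment that could show recapture is removed.

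**3. What does each missing-data method then give?**

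| Method | IGA 0-2 and IGA 0/1 recapture | EASI75 recapture |
|---|---|---|
| NRI (Section 6.4.1: missing counts as nonresponse) | 0/N = 0% | 0/N = 0% |
| mLOCF, triggering IGA kept as last value | 0/N = 0%, since 3 or more is a nonresponse on both | EASI75 status before retreatment |
| mLOCF, triggering IGA not kept | an earlier IGA, possibly 0-2, is carried forward and counted as recapture | an earlier EASI75 status |
| Observed data only | 0/0, no estimate | 0/0, no estimate |

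No cell contains information from after retreatment.

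**4. How far can the result be from the truth?** The documents give no recapture rate, so true rates of 20%, 50% and 80% were assumed. In a simulation of 20,000 retreated patients with a triggering IGA of 3 or 4, the written rules gave 0% in all three cases under NRI, and under mLOCF with the trigger kept. With censoring at retreatment lifted, the IGA 0-2 estimates were 20.1%, 49.7% and 79.6%, which are the assumed rates apart from simulation error.

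**5. Which arms?** Section 6.4's list of intercurrent events describes retreatment as following downtitration or early withdrawal, which may leave out patients rerandomised to their existing dose. Table JAHN.6.1, for safety, censors at retreatment only in arms moved to placebo or a lower dose, and follows same-dose arms to the end of the study. The rule itself makes no such distinction and says it covers safety as well.

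Suppose only the changed-dose arms are censored. Under NRI, or mLOCF with the trigger kept, those arms give 0%, and

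pooled IGA rate = (same-dose share of retreated patients) x (true rate).

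With an assumed true rate of 50%, a share of 10% gives 0.10 x 0.50 = 5%, and a share of one third gives 0.333 x 0.50 = 17%. The shares are assumptions too.

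**6. How many patients?** Section 6.1 expects about 600 patients in the substudy, and Section 5.2 rerandomises 1:1:1 with two of the three arms changing dose. That puts about 600 x 2/3 = 400 patients in arms where the rule clearly bites on retreatment. The documents do not say how many of them are expected to be retreated.

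**The case against.** The best defence is that the SAP plainly means to use data from after retreatment. It gives retreated patients their own population and table rows, Section 6.11.2 promises their response summary, and Section 6.4 opens by saying that missing-data methods depend on the estimand. This stands as evidence of intent, and a reader who infers that the sponsor planned a 0% result would be going too far. It does not waive the rule: no recapture estimand is defined, and the Period 2 rule carries no qualifier.

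A second defence is that 0% depends on an imputation the recapture row does not name. Neighbouring rows spell out NRI, mLOCF or observed data, while this one says only descriptive. Footnote c of Table JAHN.6.5 and Section 4.3 also call for observed data beyond Week 104, and the row runs to Week 200. This stands against an unconditional 0%. It does not rescue the endpoint, because observed data after censoring give no estimate.

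A third is that the mLOCF zero needs the triggering IGA to be kept. A trigger seen at an unscheduled visit might not be: Section 6.2 sends unscheduled data to listings, and the window for using such visits in Section 6.2.2 is written for Period 1. This stands as a condition on the result. If the trigger is dropped, a response from before the loss could count as recapture, which is no more informative.

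A reader might also cite Table JAHN.6.2, whose footnote b says "All analysis with censoring". That table covers selected analyses and does not list the Re-Treatment Substudy Population, so it is not relied on here.

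Finally, this is a descriptive endpoint in an unpowered substudy, and the primary objective is untouched. That limits the consequence, but recapture remains a named secondary objective.

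**Conclusion.** The point holds. A stated rule defeats a stated objective: Section 6.4 censors substudy efficacy data after retreatment with no exemption, and the recapture endpoints consist only of such data.

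- **IGA 0-2 and IGA 0/1:** 0% under NRI, and 0% under mLOCF provided the triggering IGA is the last retained value.
- **EASI75:** 0% under NRI. Under mLOCF it is frozen at pre-retreatment status, which need not be zero.
- **Observed data only:** no estimate.

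At minimum this applies to the placebo and downtitrated arms. The stronger statement that recapture is 0% in every arm under any method is tempting, but the documents do not support it: the method is not named in the row, and the position of same-dose arms is unclear. The conclusion assumes that no exemption sits in the main protocol, which the SAP and the addendum cite but which is not among these documents. The most likely explanation is an omitted sentence.

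**What to change.** In Section 6.4, and in the recapture row of Table JAHN.6.5, state that the retreatment part of the Period 2 censoring rule does not apply to recapture analyses of the Re-Treatment Substudy Population. For those analyses specify:

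- censoring only at permanent study drug discontinuation;
- time zero at the first retreatment dose;
- only assessments after retreatment count;
- patients with no observed response within 16 weeks are nonresponders, and no pre-retreatment value is carried forward;
- results presented by rerandomised arm.

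Because Table JAHN.6.5 lists only IGA of 2 or lower, the wording should also name IGA 0/1 and EASI75.

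Reconcile Section 6.4 with Table JAHN.6.1 on whether same-dose arms are censored at retreatment. If recapture tables have already been produced at an earlier lock, record which rule they used.

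The cost is a few lines of SAP text and one programming flag. No new data are needed, and the clinical retreatment rule is not changed.

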- **Screening and baseline period:** Screening should occur during the last visit of the originating study unless the patient received oral systemic AD treatment as rescue therapy during the originating study and needs additional time to complete the required 4-week washout period or the sponsor gave approval.
- **Treatment Period 1:** Treatment period from Week 0 to Week 52. Patients will be classified as responders, partial responders or nonresponders at the entry of Study JAHN based on the criteria given in Section 5.1.

- Treatment Period 2: Treatment period from Week 52 to 200 and will contain a randomized withdrawal and downtitration substudy. At Week 52, all patients will be evaluated for substudy eligibility, and the criteria are given in the Protocol. Patients not entered in the substudy will continue on their current treatment.
- Posttreatment follow-up period: Period from Week 200 (Visit 22) or Early Termination Visit (ETV) to approximately 28 days after the last dose of IP.

Abbreviations: BARI = baricitinib; IGA = Investigator’s Global Assessment; TCS = topical corticosteroids.

a Background TCS may be initiated or reinitiated at any time during the study, following the guidelines in the Protocol (Section 7.7.1) and will be provided as part of rescue or retreatment any time a patient’s IGA score becomes ≥ 3 as described in the Protocol (Sections 5.1.2.1 and 5.1.3.1).

b Eligible patients will be rerandomized in the withdrawal and downtitration substudy as described in the Protocol (Section 5.1.3.1). Patients who do not enroll in the substudy will remain on their treatment.

c Patients enrolled in the substudy will automatically be retreated if their IGA score becomes ≥ 3 as described in the Protocol (Section 5.1.3.1).

d Rescue is available as described in the Protocol (Section 5.1.2.1).

Figure JAHN.5.1. Illustration of study design for Clinical Protocol I4V-MC-JAHN.

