BARI 2 mg	BARI 2 mg followed to end of Treatment Period 1 or censored at dose or treatment change
PBO/BARI 1 mg/BARI 2 mg to BARI 4 mg	PBO/BARI 1 mg/BARI 2 mg switching to BARI 4 mg at entry to Study JAHN followed to end of Treatment Period 1 or censored at dose or treatment change
BARI 4 mg	BARI 4 mg followed to end of Treatment Period 1 or censored at dose or treatment change
Pooled BARI	BARI 1 mg/BARI 2 mg/BARI 4 mg at entry to Study JAHN followed to end of Treatment Period 1 or censored at dose or treatment change
Treatment Groups for Treatment Period 2 (Week 52-200)	Definition
BARI 2 mg to PBO	Randomized to PBO in Treatment Period 2 (previously treated with BARI 2 mg) followed to end of study or censored at retreatment with BARI 2 mg

Treatment Groups for Treatment Period 2 (Week 52-200)	Definition
BARI 2 mg to BARI 1 mg	Randomized to BARI 1 mg in Treatment Period 2 (previously treated with BARI 2 mg) followed to end of study or censored at retreatment with BARI 2 mg
BARI 2 mg to BARI 2 mg	Randomized to stay on BARI 2 mg in Treatment Period 2 followed to end of study
BARI 4 mg to PBO	Randomized to PBO in Treatment Period 2 (previously treated with BARI 4 mg) followed to end of study or censored at retreatment with BARI 4 mg
BARI 4 mg to BARI 2 mg	Randomized to BARI 2 mg in Treatment Period 2 (previously treated with BARI 4 mg) followed to end of study or censored at retreatment with BARI 4 mg
BARI 4 mg to BARI 4 mg	Randomized to stay on BARI 4 mg in Treatment Period 2 followed to end of study
BARI 2 mg	Not part of the substudy, stayed on BARI 2 mg in Treatment Period 2 followed to end of study (this treatment group includes the open-label BARI 2 mg addendum patients)
BARI 4 mg	Not part of substudy, stayed on BARI 4 mg in Treatment Period 2 followed to end of study
Treatment Group for Treatment Periods 1 and 2 (Week 0-104) (for Box Plots Only)	Definition
PBO	Placebo at entry to Study JAHN followed to end of study or censored at treatment change
BARI 1 mg	BARI 1 mg followed to end of study or censored at dose or treatment change
BARI 2 mg to PBO	BARI 2 mg in Treatment Period 1, rerandomized to PBO in Treatment Period 2 followed to end of study or censored at retreatment with BARI 2 mg
BARI 2 mg to BARI 1 mg	BARI 2-mg in Treatment Period 1, rerandomized to BARI 1 mg in Treatment Period 2 followed to end of study or censored at retreatment with BARI 2 mg

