6.14. Safety Analyses

Detailed analyses and discussion of Study JAHN safety data are more thoroughly assessed in the context of combining the safety data from the originating Studies, JAHL, JAHM, and JAIY with the safety data from Study JAHN. The planned analyses are described in the compound level safety standards.

For the purpose of Study JAHN alone, the following are planned to be analyzed:

- duration of exposure by Treatment Periods 1 and 2
- overview of AEs by Treatment Periods 1 and 2
- treatment-emergent adverse events (TEAEs) by PT nested within System Organ Class (SOC) by Treatment Periods 1 and 2
- serious adverse events (SAEs) by PT nested within SOC by Treatment Periods 1 and 2, and listing of SAEs in Treatment Periods 1 and 2 combined (one listing)
- AEs leading to permanent study drug discontinuation by PT nested within SOC for Treatment Period 1, and listing of AEs leading to permanent study drug discontinuation and discontinuation from the study in Treatment Periods 1 and 2 combined (one listing)
- listing of deaths in Treatment Periods 1 and 2 combined (1 listing), if any
- clinical laboratory evaluation and vital signs in terms of box plots, descriptive and treatment-emergent summaries in Treatment Period 1
- clinical laboratory and vital signs in terms of box plots and descriptive summaries in Treatment Periods 1 and 2 combined

The general methods used to summarize safety data, including the definition of baseline value, are described in Section 6.2.

Safety analyses will be conducted according to the safety population defined in Section 6.2.1 and the treatment groups defined in Table JAHN.6.1 in Section 6.2.1.

Unless otherwise specified, by-visit summaries will include planned on-treatment visits. For tables that summarize events (such as AEs), on-treatment and follow-up data will be included up to 30 days after the last dose of treatment or up to dose or treatment change, where applicable.

For the February 2021 DBL and Final DBL summary and analyses, safety analyses will be done for the disposition summary and the below AE tables summarized in Period 1 and Period 2, respectively. Other detailed safety assessments will be implemented in the integrated safety analysis plan with other studies (I4V-MC-JAIN, I4V-MC-JAIW, and I4V-MC-JAIX).

- overview of AEs
- TEAEs
- AEs leading to permanent discontinuation of study drug
- SAEs

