6.14.2. Adverse Events

Adverse events are recorded in the eCRFs. Each AE will be coded to SOC and PT using the MedDRA version that is current at the time of DBL. Severity of AEs is recorded as mild, moderate, or severe. TEAEs will be analyzed by Treatment Periods 1 and 2.

A TEAE is defined as an event that first occurred or worsened in severity after the first dose of study treatment in Study JAHN and on or prior to the last visit date during the analysis period. The analysis period is defined as the treatment period plus up to 30 days off-drug follow-up time.

Adverse events are classified based upon the MedDRA PT. The MedDRA Lowest Level Term (LLT) will be used in defining which events are treatment emergent. The maximum severity for each LLT during the baseline period up to first dose of the study medication in Study JAHN will be used as baseline. If an event with missing severity is preexisting during the baseline period, and persists during the treatment period, then the baseline severity will be considered mild for determining treatment emergence (ie, the event is treatment emergent if the severity is coded moderate or severe postbaseline and not treatment emergent if the severity is coded mild postbaseline). If an event occurring postbaseline has a missing severity rating, then the event is considered treatment emergent unless the baseline rating is severe, in which case the event is not treatment emergent. The day and time for events where onset is on the day of the first dose of study treatment will both be used to distinguish between pretreatment and posttreatment in order to derive treatment-emergence. Should there be insufficient data for AE start date to make this comparison (eg, the AE start year is the same as the treatment start year, but the AE start month and day are missing), the AE will be considered treatment emergent.

In general, summaries will include the number of patients in the safety population (N), frequency of patients experiencing the event (n), and relative frequency (ie, percentage; $n/N*100$). For any events that are gender specific based on the displayed PT, the denominator used to compute the percentage will only include patients from the given gender.

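### SAP Section 6.4 extends an efficacy censoring rule to substudy safety. This conflicts with the 30-day event window in all arms and, read literally, with the follow-up set for the continued-dose arms.

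*SAP*

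**What the plan says.** SAP Section 6.4 defines the Period 2 censoring rule as one that "will censor efficacy data after permanent study drug discontinuation or after retreatment, whichever occurs first". The next sentence sets its scope: "This censoring rule will be applied to efficacy endpoints and safety conducted for the Period 2 population corresponding to the withdrawal and downtitration substudy". No arm is exempted.

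Other sections set safety follow-up differently:

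- **Table JAHN.6.1 (Section 6.2.1), continued-dose arms.** The definitions are "Randomized to stay on BARI 2 mg in Treatment Period 2 followed to end of study" and "Randomized to stay on BARI 4 mg in Treatment Period 2 followed to end of study", with no cut at retreatment.
- **Table JAHN.6.1, arms moved to placebo or a lower dose.** Patients who came from 2 mg are "followed to end of study or censored at retreatment with BARI 2 mg". Those who came from 4 mg have the matching wording.
- **Section 6.14.** For event tables, "on-treatment and follow-up data will be included up to 30 days after the last dose of treatment or up to dose or treatment change". The last clause holds only in cases to which it applies.
- **Section 6.14.2.** For treatment-emergent events, "The analysis period is defined as the treatment period plus up to 30 days off-drug follow-up time".
- **Section 6.14.1.** Exposure ends at the last date on drug, or at a dose or treatment change according to the Section 6.2.1 groups.

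On who is retreated, footnote c to Figure JAHN.5.1 says "Patients enrolled in the substudy will automatically be retreated if their IGA score becomes" 3 or more. Section 6.2.1 describes retreatment as being at the original dose. Section 6.2.2 limits the Period 2 safety analyses to adverse events.

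**The concern.** A programmer who applies Section 6.4 and one who applies Table JAHN.6.1 with Section 6.14 would build different Period 2 adverse event tables from the same data.

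The first difference touches every arm. Cutting safety at permanent discontinuation discards the off-drug window. Section 5.1 places the post-treatment follow-up about 28 days after the last dose, so the events lost are ones that the study set out to collect.

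The second touches the patients randomized to stay on 2 mg or 4 mg. Retreatment at the original dose changes nothing in their baricitinib exposure, yet under Section 6.4 their events would stop counting at the first IGA of 3 or more. Their exposure under Section 6.14.1 would continue. Numerator and denominator would then cover different periods, and the error would favour the drug.

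**Working it through.** The plan states no figure that depends on this rule, so there is nothing to reproduce. The check is a comparison of text, followed by an illustration.

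**Side by side**

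| Situation | Section 6.4, read literally | Table JAHN.6.1 with 6.14 and 6.14.2 | Result |
|---|---|---|---|
| Permanent discontinuation, any arm | Safety cut at discontinuation | Events counted to 30 days after last dose | Conflict |
| Retreatment, arm moved to placebo or lower dose | Cut | Cut | Agree |
| Retreatment, arm kept on 2 mg or 4 mg | Cut | Followed to end of study | Conflict |

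The dose-or-treatment-change clause in Section 6.14 does not settle the third row, because retreatment at the original dose is not a dose change in those arms.

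**Upper bound for the 30-day window.** Section 6.1 expects about 600 substudy patients and Section 5.2 allocates 1:1:1, so about 600/3 = 200 are in the two continued-dose arms together. If every patient contributed a full 30 days, the window would hold 600 × 30/365.25 = 49.3 patient-years overall and 200 × 30/365.25 = 16.4 in the continued-dose arms.

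**Illustration for retreatment in a continued-dose arm**

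Assumptions:

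- 20% discontinue per 52 weeks, borrowed from the 80% completion that protocol Section 4.8.1 expects in Weeks 0 to 52.
- A proportion p of 20%, 40% or 60% is retreated per 52 weeks. This is not in the documents.
- Both hazards are constant.

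Formulas:

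- Discontinuation hazard d = −ln(0.8)/52 = 0.00429 per week.
- Retreatment hazard r = −ln(1 − p)/52, which is 0.00982 per week for p = 40%.
- Mean follow-up over H weeks = (1 − exp(−hH))/h, with h = d without the retreatment cut and h = d + r with it.

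| Horizon | No cut at retreatment | p = 20% | p = 40% | p = 60% |
|---|---|---|---|---|
| Week 104 (H = 52) | 46.6 weeks | 41.9 (10% lost) | 36.8 (21% lost) | 31.0 (33% lost) |
| Week 200 (H = 148) | 109.6 weeks | 83.8 (24% lost) | 62.1 (43% lost) | 43.9 (60% lost) |

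**Effect on a rate.** Assume 5 events per 100 patient-years (not in the documents), 100 patients, p = 40% and follow-up to Week 200.

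- Full follow-up: 109.6 × 7/365.25 = 2.10 years per patient, or 210 patient-years and 10.5 events.
- Events counted only to retreatment: 62.1 × 7/365.25 = 1.19 years per patient, or about 6 events.
- If the exposure denominator stays at 210 patient-years, the apparent rate is 5.95/210 = 2.8 per 100 patient-years instead of 5.

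**The case against.** The best defence is that the words 'and safety' are a stray phrase and that the safety sections govern. Section 6.2.1 sends the final-lock adverse event tables to the Table JAHN.6.1 groups, and Section 6.14 does the same for safety generally. The sentence defining the Period 2 rule speaks of efficacy data only, as do the Period 1 and non-substudy rules beside it. A slip is therefore plausible. But no section says that Table JAHN.6.1 overrides Section 6.4, whose scope sentence names safety outright, so the text still needs correcting.

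The retreatment limb is also open to question. The list of intercurrent events in Section 6.4 speaks of retreatment after downtitration or early withdrawal, which fits only the arms whose dose was reduced or stopped. Footnote c defers to main protocol Section 5.1.3.1, which is not among the documents reviewed, so how retreatment is recorded in a continued-dose arm cannot be confirmed. That softens the retreatment conflict. It leaves the 30-day conflict untouched.

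A reader might go further and infer three things that the documents do not support:

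- **That serious events and deaths would vanish.** Section 6.14 lists serious events across both periods, and Section 6.14.2.2 lists deaths whenever they occurred in the study. The loss is from the by-arm tables.
- **That reported patient-years would shrink by the percentages above.** Section 6.14.1 fixes exposure separately and does not cut it at retreatment on an unchanged dose. The likelier harm is a mismatch between events and exposure.
- **That the continued-dose substudy arms carry the long-term safety evidence alone.** Table JAHN.6.1 also follows non-substudy 2 mg and 4 mg groups, Section 6.2.1 plans an all-baricitinib analysis, and Section 6.14 places detailed safety assessment in integrated analyses.

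**Conclusion.** The inconsistency is real and should be corrected. The conflict over discontinuation and the 30-day window holds in all arms on the plain text. The conflict over retreatment in the continued-dose arms holds on a literal reading of Section 6.4 with footnote c and the original-dose definition. There is no retreatment conflict in the placebo and lower-dose arms.

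The consequence is confined to the Period 2 by-arm adverse event tables and to any rate formed by setting their counts against the reported patient-years. Section 6.14.2 plans percentages of patients. These would be lowered directly wherever a patient's only event fell after the cut.

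The size cannot be derived from the documents. The illustrated 21% loss to Week 104 (range 10% to 33%) rests on assumed retreatment rates and on a discontinuation rate borrowed from a different period and population. The Week 200 figures are weaker still: they extrapolate constant hazards, and the phased site closure described for SAP Version 8 makes a full 148 weeks an upper bound. The event rate of 5 per 100 patient-years is hypothetical. The textual conflict depends on none of these numbers.

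**What to change.** In SAP Section 6.4, delete 'and safety' from the scope of the Period 2 censoring rule. Add one sentence saying that substudy safety follow-up is governed by Table JAHN.6.1 and Sections 6.14, 6.14.1 and 6.14.2, and that event counts and patient-years use the same cut-off in each arm. If on-treatment exposure is kept as the denominator while events are counted for 30 days off drug, say so explicitly.

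The cost is a wording change and a check that the Period 2 adverse event programs follow it. It needs no new data and does not affect patient management. If tables have already been produced under Section 6.4 as written, they would need to be rerun.
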